6.9.8 Laboratory Evaluations

Data for the following hematology, serum chemistry, lipid profile, and urinalysis analytes received from the central laboratory will be listed and summarized by treatment group and visit (Table 6.9-1). If data for any additional analytes are also received then these will be listed only.

Statistical Analysis Plan

Version: Final 1.0

Lexicon Pharmaceuticals Protocol No. LX 4211.1-312-T1DM

Date of Issue: 17 MAR 2017

Covance Study ID: 000000145143

Table 6.9-1 Central Laboratory Assessments

| Hematology | Serum Chemistry | Lipid Profile | Urinalysis |
|--|--|---|--|
| Complete blood count (CBC) Differential Platelet count Hemoglobin Hematocrit | Sodium Potassium Chloride Carbon dioxide (bicarbonate) BUN Creatinine Glucose (serum) ALT AST Total bilirubin Alkaline phosphatase (ALP) Uric acid Calcium Phosphorus Total protein Albumin Magnesium Creatine phosphokinase (CPK) Lactate dehydrogenase (LDH) | Total cholesterol Triglycerides HDL-C LDL-C Non-HDL-C | Urine albumin Urine calcium Urine glucose Urine creatinine Urine pregnancy test Urine dipstick with microscopy: Specific gravity pH Protein Blood Ketones Bilirubin Urobilinogen Nitrate Leukocyte esterase |
| Other Blood Samples | | | |
| A1C FPG Serum pregnancy test - females only Follicle-stimulating hormone (FSH) - if necessary to confirm postmenopausal status BHB Anion gap Thyroid stimulating hormone (TSH) | | | |

All summaries of laboratory test results will be presented in International System of Units (SI) and conventional units. Out-of-reference-range values will be flagged as high (H) or low (L) in the listings.

For analysis purposes, values preceded by a “<” or a “>” sign (ie those below or above the limits of quantification) will be considered equal to the lower or upper limit of quantification, respectively.

Laboratory evaluations measured on a continuous scale will be summarized by visit using standard descriptive statistics for the Safety population. Changes from Baseline will also be summarized. For analysis by visit, analysis windowing as described in [Section 5.1](#) will be utilized for each scheduled visit such that unscheduled visit will also be considered. For each laboratory analyte, the Baseline value will be defined as last scheduled or unscheduled value collected prior to the first dose of treatment.

The incidence rate of patients with diabetic specific laboratory results during the Double-blind Treatment Period will be presented for the following abnormality values:

- BHB >0.6, >1.0, >2.0, and >3.0 mmol/L
- Serum sodium >150 mEq/L
- Blood hematocrit >55%

Statistical Analysis Plan

Version: Final 1.0

Lexicon Pharmaceuticals Protocol No. LX 4211.1-312-T1DM

Date of Issue: 17 MAR 2017

Covance Study ID: 000000145143

- Decrease from Baseline in eGFR $\geq 25\%$

For hematology and serum chemistry, shift tables presenting movement in and out of reference range from Baseline to each scheduled post-Baseline visit will be provided for each treatment group.

Mean change from Baseline with standard error bars will be plotted by visit for select laboratory parameters for the Safety population.

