8.3.1 General Guidelines

The timing of the visits and follow-up telephone contacts for this trial are given relative to the day of randomization. The patients should be encouraged to return for their visits as close to the scheduled visit date as possible. Patients should be encouraged to fast (with the exception of water or noncaffeinated, zero-calorie beverages) for at least 8 hours before collection of any fasting laboratory samples. If the patient is unable to fast as above, the scheduled “fasting” laboratory samples will still be collected and the non-fasting status will be noted in the eCRF and on the laboratory requisition form. ALL data collected will be used in the evaluations, including data that may originate outside the investigative site, such as non-visit (unscheduled) clinical laboratory evaluations.

Any events that occur between scheduled visits should be recorded by the Investigator as soon as they come to his or her attention.

Note: If serum creatinine increases by $\geq 30\%$ above the Baseline value during the study, then the Investigator should consider assessment of: volume status, diuretic dosage, discontinuing NSAIDs, and other relevant testing including renal imaging techniques, as appropriate.

Sodium-glucose cotransporter type 2 inhibitors are associated with osmotic diuresis and volume depletion, which may lead to dizziness or hypotension, especially in the elderly. All patients will be advised to maintain proper fluid intake and to consider increasing it if they sense greater thirst, more urine production, or if they feel dizzy or faint. Investigators should consider closer monitoring of renal function in patients assessed to be at risk for deterioration of renal function. This may include evaluation of relevant laboratory tests at an unscheduled visit a week after initiating double-blind study drug.

Visits should be scheduled in the morning, at approximately the same time of day.

Prior to each visit, patients should be contacted and reminded of the date and time of their appointment.

In addition, the patient should be instructed to:

1. Bring the study drug bottles (used and unused) to the clinic. **Note:** Patients should not take study drug on the day of the visit until instructed by site staff. Patients should be instructed to take their basal insulin on the day of the visit, but not to take bolus insulin on the day of the visit until instructed by site staff.

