5 DATA HANDLING

5.1 Time Points and Visit Windows

Day 1, defined as the Baseline/Randomization visit, is also the first day that study treatment is planned to be started. Should study treatment start at a later date, Day 1 will be defined as the date that study treatment is initiated. Relative days after Day 1 are calculated as (assessment date – Day 1 date) + 1. Relative days prior to Day 1 are calculated as (assessment date – Day 1 date). The day prior to Day 1 is Day -1; there is no Day 0.

The following visit windows defined in [Table 5.1-1](#) will be used for the by-visit analyses of the primary endpoint, the secondary and other endpoints. All other analyses will use the nominal study visit as defined in the Study Schedule and eCRF.

In general, the Baseline value for a variable is defined as the last value collected or taken on or before Day 1, prior to the first dose of double-blind study drug. In cases where there are multiple such values, the non-missing value closest to the start of study treatment is selected. If time is available for an assessment on Day 1, it will be compared with dosing time on Day 1 to define the Baseline value.

If there are multiple visits (scheduled or unscheduled) within a visit window, the measurement closest to the target day of the visit will be used in the analysis. If the measurements are equally distant to the target day, then the later one will be used in the analysis. An exception to these rules applies to the variable hypoglycemic events per patient per day by SMBG, where a scheduled visit takes precedence over an unscheduled visit. Hypoglycemic events by SMBG are based on the data entered in a patient's study diary, and hence, it is more appropriate to choose the scheduled visit when a patient would typically return the diary to the site over an unscheduled visit.

Statistical Analysis Plan

Version: Final 1.0

Lexicon Pharmaceuticals Protocol No. LX 4211.1-312-T1DM

Date of Issue: 17 MAR 2017

Covance Study ID: 000000145143

Table 5.1-1 Definition of Visit Windows

| Visit | Target Day of Visit ^a | A1C, Insulin, Hypoglycemic Events per Day by SMBG, Body Weight, Vital Signs, FPG, Serum Chemistry, Beta-hydroxy Butyrate (BHB) | Urinalysis, Urine Albumin, Urine Calcium, Urine Glucose, Urine Creatinine, PSDD-NRS ^b | Fasting Lipid Profile, Hematology |
|--------------------------------|----------------------------------|--|--|-----------------------------------|
| 1 Baseline ^c | 1 | ≤1 | ≤1 | ≤1 |

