| 2 Week 4 | 29 | 2-43 | -- | -- |
| 3 Week 8 | 57 | 44-85 | -- | 2-113 |
| 4 Week 16 | 113 | 86-141 | -- | -- |
| 5 Week 24 | 169 | ≥142 | ≥2 | ≥114 |

(a) Relative to the date of Baseline/Randomization visit (Day 1)

(b) For Satiety substudy population only.

(c) If time is available for an assessment on Day 1, it will be compared with dosing time on Day 1 to define Baseline value.

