| | - | ±3 | - | ±3 | ±3 | ±3 | ±3 | +7 |
| Fasting blood sample and random urine for storage | | | X | | | | X | |

A1C = hemoglobin A1C; ADA = American Diabetes Association; AE = adverse event; BHB = beta-hydroxy butyrate; BP = blood pressure; EASD = European Association for the Study of Diabetes; eCRF = electronic case report form; DKA = diabetic ketoacidosis; ECG = electrocardiogram; EOSI = Events of Special Interest; EOT = End of Treatment; EW = early withdrawal; IXRS = Interactive Voice/Web Response System; SAE = serious adverse event; SMBG = self-monitored blood glucose; Wk = Week

- a. The duration of the single-blind placebo Run-in Period is 14 days, ±3 days.
- b. All laboratory assessments occur prior to first dose of Double-blind study drug. All visit dates will be scheduled based on the date of randomization with a ±3 days visit window allowed.
- c. All patients will have a follow-up telephone contact 30 days after the last dose of study drug to collect information on any SAEs, any EOSI, or AEs that were ongoing at the time of the EOT/EW Visit.
- d. A complete physical examination will include, at minimum, a review of the patient's general appearance, head, eyes, ears, nose and throat, neck, heart, lungs, abdomen, back and extremities, skin, and general neurological system. A symptom related brief physical exam will only occur if the patient is experiencing symptoms or AEs. If a symptom related brief physical exam is required, it should include a review of all body systems that relate to the symptoms and/or AE the patient is experiencing.
- e. Patients should be weighed at approximately the same time of day, wearing minimal clothing, ie, no coat/shoes, using the same calibrated scale where possible.
- f. Vital sign measurements should be measured after the patient has been seated for at least 5 minutes and prior to phlebotomy.
- g. The 12-lead ECG recordings should be obtained prior to the morning study drug administration. ECG recording should be recorded either prior to phlebotomy or at least 30 minutes after phlebotomy.
- h. The patient will be provided with a study diary and glucose monitoring supplies for use at home. These supplies will be provided to all sites by the Sponsor.
- i. After the initial dispensation at the Screening Visit, additional Ketostix[®] (or similar) will be dispensed on an as needed basis.
- j. Counseling frequency may be increased at the discretion of the Investigator.

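### Hematology and chemistry shift tables in SAP 6.9.8 take one value per visit, so interim out-of-range results are usually left out of the by-arm laboratory tables for most analytes

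*SAP*

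**What the plan says.** SAP 6.9.8 summarizes the central-laboratory analytes in Table 6.9-1. Its plan for the blood-count and chemistry panels is that "shift tables presenting movement in and out of reference range from Baseline to each scheduled post-Baseline visit will be provided for each treatment group". For by-visit laboratory summaries, the same section says that the windows of SAP 5.1 "will be utilized for each scheduled visit such that unscheduled visit will also be considered". Within a window, "the measurement closest to the target day of the visit will be used in the analysis", and a tie goes to the later value. SAP 5.1 also has a general rule for analyses outside its list of by-visit endpoints: "All other analyses will use the nominal study visit as defined in the Study Schedule and eCRF". The shift-table sentence does not say which rule it follows.

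Counts over the whole treatment period are planned in two places:
- SAP 6.9.8: BHB at four cut-offs, sodium above 150 mEq/L, hematocrit above 55%, and a fall in eGFR of at least 25%.
- SAP 6.9.7: ALT, AST and total bilirubin, taken from laboratory data whether or not the investigator reported an event.

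Other out-of-range values are flagged high or low in listings.

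Protocol 8.3.1 says that everything collected will enter the evaluations, "including data that may originate outside the investigative site, such as non-visit (unscheduled) clinical laboratory evaluations". On closer renal monitoring of at-risk patients it adds: "This may include evaluation of relevant laboratory tests at an unscheduled visit a week after initiating double-blind study drug".

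**The concern.** A shift table built on one value per visit shows where patients stood near the target day. It does not show whether a patient went out of range between visits. A value that was abnormal and then corrected drops out if a later or better-timed result fills the slot.

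The protocol names osmotic diuresis and volume depletion as class effects (7.4, 8.3.1). It makes volume depletion, renal events and DKA events of special interest (9.5), and serum bicarbonate is one of its tabulated DKA criteria (9.5.2). Interim bicarbonate, potassium or BUN values outside range are therefore relevant to safety. If they appear only in listings, nobody can read off how many patients in each arm had one.

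**Working it through.** **1. Reproduce the SAP windows.** Target days are 29, 57, 113 and 169 (SAP Table 5.1-1). Midpoints between neighbouring targets:
- Chemistry: (29+57)/2 = 43; (57+113)/2 = 85; (113+169)/2 = 141.
- Hematology, sampled after Baseline only at Weeks 8 and 24: (57+169)/2 = 113.

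These match the printed limits; the Week 8 row reads "3 Week 8 | 57 | 44-85 | -- | 2-113".

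**2. Apply the selection rule to a week-1 test.** The SAP has no Day 0, so one week after Day 1 is Day 8. SAP Appendix 1 says "All visit dates will be scheduled based on the date of randomization with a" window of 3 days either side, so an on-schedule Week 4 visit falls on Days 26-32.
- Chemistry: |8-29| = 21 days, against at most 3 for the scheduled visit. Day 8 also loses to any other value on Days 9-43, since |9-29| = 20 and |43-29| = 14. It is used if it is the only value in Days 2-43, or if the only others fall on Days 2-7.
- Hematology: |8-57| = 49 days, against at most 3 for a visit on Days 54-60.

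**3. When can any unscheduled value take the slot?** With the scheduled visit within 3 days of target, the largest number of other days in the window that would displace it is:

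| Window | Other days in window | Most days that displace the visit | If visit is on target |
|---|---|---|---|
| Chemistry Week 4 (2-43) | 41 | 6 | 0 |
| Chemistry Week 8 (44-85) | 41 | 6 | 0 |
| Chemistry Week 16 (86-141) | 55 | 6 | 0 |
| Hematology Week 8 (2-113) | 111 | 6 | 0 |

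An abnormal value on Day 26 with a normal repeat on Day 29 loses its place (3 days against 0). So does Day 28 followed by Day 30 (tied at 1 day; the later is used). Under the nominal-visit rule, unscheduled values would not enter at all. Either reading leaves one value per visit.

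**4. Count the rows with no whole-period table (Table 6.9-1, rows as printed).**
- Chemistry: 19 rows, less sodium, creatinine (through eGFR), ALT, AST and total bilirubin: 19 - 5 = 14.
- Hematology: 5 rows, less hematocrit: 5 - 1 = 4.
- Together: 18/24 = 75%.

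**5. Check whether eGFR covers creatinine.** In SAP 6.8.4.13, eGFR varies as creatinine to the power -1.154.
- A 30% creatinine rise, the level flagged in Protocol 8.3.1: 1 - 1.30^(-1.154) = 0.261, a 26.1% fall in eGFR.
- Creatinine ratio for a 25% fall: 0.75^(-1/1.154) = 1.283, a rise of about 28.3%.

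A patient who reaches the protocol's creatinine level therefore also reaches the SAP's eGFR threshold.

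**The case against.** A reader might infer that the week-1 check never reaches a by-arm table, or that the arms cannot be compared on early volume and acidosis signals. The documents do not support either reading.
- The week-1 test is optional, is for patients judged at renal risk, and is renal in purpose. Its creatinine result reaches the eGFR table (step 5).
- An interim value is used when it is the only one, or the closest one, in its window.
- Protocol 9.1 has clinically significant abnormal results recorded as adverse events. These are tabulated by arm (SAP 6.9.1). Volume depletion, renal events and DKA with metabolic acidosis are summarized by arm as events of special interest (SAP 6.9.2), and acidosis-related events have their own by-arm tables (SAP 6.9.6).
- No clinical passage names transient potassium, magnesium or blood-count changes as expected early effects.

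Nor is this a clear breach of the protocol. Using all data in the evaluations does not promise that each value enters a shift table. Protocol 10.4.3 relies on descriptive statistics and patient listings, and asks for shift tables without specifying worst values.

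Two further points stand. The 18 rows include analytes of little relevance here, such as total protein and LDH. The long hematology window mainly reflects sampling at Weeks 8 and 24 only.

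These points narrow the gap but do not close it. The adverse event route depends on the investigator's judgment of significance. For liver tests the SAP chose not to depend on that judgment, and it also plots each patient's maximum ALT, AST and bilirubin.

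**Conclusion.** The point holds in a limited form. Interim out-of-range values are usually left out of the by-arm laboratory tables, and 18 of 24 hematology and chemistry rows (75%) have no whole-period table to catch them. Most of the six covered rows are counted at fixed thresholds or in one direction only. The values lost to by-arm comparison are those not reported as adverse events and not crossing a fixed threshold.

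The number of patients affected cannot be derived, because the documents do not say how many unscheduled tests to expect. The 75% counts table rows, not missed abnormalities.

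The conclusion assumes that the SAP 6.9.8 incidence table uses unscheduled as well as scheduled values, which the text does not say expressly, and that it is split by arm under the general rule in SAP 6.1. If unscheduled values are excluded, the interim creatinine result is not covered either. Sample size, alpha, power and efficacy analyses are untouched. This is a cheap improvement.

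**What to change.** Keep the by-visit tables. Add to SAP 6.9.8, for hematology and serum chemistry, by treatment group in the Safety population, shift tables from Baseline to each patient's lowest and highest post-Baseline value during the Double-blind Treatment Period. Use all scheduled and unscheduled central-laboratory results. Leave outside-site results in listings unless their reference ranges are held: SAP 6.9.8 summarizes central-laboratory data, and mixing laboratories would blur a reference-range shift. State in the same edit that the existing incidence table uses unscheduled values, if that is the intention.

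Coverage rises from 6 to all 24 rows. The cost is one extra table program on central-laboratory data already collected.

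The downside is that worst-value counts rise with the number of tests. Unscheduled tests may also be prompted by symptoms, possibly more often in one arm. Show the number of tests per patient by arm beside the table and treat it as descriptive. This discloses an imbalance in testing but does not correct for it.

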6.9.9 Vital Signs

The following vital signs will be listed and summarized by treatment group and visit.

- sitting SBP and DBP (mm Hg)
- pulse rate (bpm)
- respiration rate (breaths/min)
- body temperature ($^{\circ}\text{C}$)

Vital signs data and changes from Baseline in vital signs will be summarized by visit using standard descriptive statistics for the Safety population. The Baseline value will be defined as last scheduled or unscheduled value collected prior to the first dose of treatment. For analysis by visit, analysis windowing as described in [Section 5.1](#) will be utilized for each scheduled visit such that unscheduled visit will also be considered.

6.9.10 Electrocardiograms

The ECG Core Laboratory will review protocol-scheduled ECGs to assess the presence of Q-waves (ie, potential “silent” MI) and/or left bundle branch block (LBBB). Any new incidence of Q-wave or LBBB identified by the ECG Core Laboratory will be considered a possible unreported MI. The assessments recorded on the final “outcome” ECG Core Laboratory Assessment Forms will be used for the analysis.

The following qualitative ECG measurements will be listed and summarized by treatment group and visit for the Safety population:

- Presence of Q-waves
- New Q-waves
- Presence of LBBB
- New LBBB

6.9.11 Physical Examination

Physical examination results (normal or abnormal) and details of abnormalities will be listed for each patient.

For each physical examination body system, the number and percentage of patients with abnormalities at Baseline and post-Baseline will be summarized by treatment group for the Safety Population.

7 CHANGES IN THE PLANNED ANALYSES OF THE PROTOCOL

- The protocol (Section 10.3.1.3) stated that the secondary endpoints (A1C, body weight, SBP, and bolus insulin dose) will be assessed at specified cut points. The specific cut points to use are provided in this SAP (see [Section 3.1.3](#)).

Statistical Analysis Plan

Version: Final 1.0

Lexicon Pharmaceuticals Protocol No. LX 4211.1-312-T1DM

Date of Issue: 17 MAR 2017

Covance Study ID: 000000145143

- Sensitivity analysis of the primary efficacy endpoint using the Last Observation Carried Forward (LOCF) algorithm to impute missing data will not be performed. The analysis of the primary efficacy endpoint will use NRI to impute missing data at Week 24 (see [Section 5.2.1](#)).
- Two sensitivity analyses of the primary efficacy endpoint using the same cut-off dates for SH and DKA events have been added (see [Section 6.8.2](#)).
- Summary statistics of mean bolus insulin dose, total daily insulin dose, and mean daily basal (or non-bolus) insulin dose as percent of the Baseline measure will be provided, as stated in [Sections 6.8.3.4](#) and [6.8.4.8](#).
- Analysis of the primary efficacy endpoint and the change from Baseline to Week 24 in A1C will be performed for the subgroups defined by age at study entry (<75 years, ≥75 years), sex, race, and Week -2 A1C (≤8.5%, >8.5%).
- Analysis of SBP change from Baseline to Week 16 will be performed for the subgroups defined by Baseline SBP <130 mm Hg, <140 mm Hg, and ≥ 140 mm Hg.
- EOSI events will be summarized by treatment groups across all patients (planned) and for the subgroups determined by use of CSII at Screening (Yes, No).
- For EOSIs of Malignancies of special interest, “thyroid” has been added to the list of malignancies in [Section 6.9.2](#).
- Amputations have been added to the EOSIs specifically listed in [Section 6.9.2](#) (note: per Section 9.5 of the protocol, AEs other than the EOSIs listed in the protocol may be determined to be of special interest).
- Additional overall summaries will be presented for EOSI for 3 time periods described in [Section 6.9.2](#).
- Incidence of BHB >0.6 mmol/L during Double-blind Treatment Period will be analyzed by logistic regression models.
- Incidence of treatment-emergent acidosis-related AEs will be analyzed.

9 APPENDICES

Appendix 1 - Schedule of Events

Statistical Analysis Plan

Version: Final 1.0

Lexicon Pharmaceuticals Protocol No. LX 4211.1-312-T1DM

Date of Issue: 17 MAR 2017

Covance Study ID: 000000145143

Main Study Schedule of Assessments

| Week/Visit Window (days) | Screening | Single-blind Placebo Run-in | Double-blind Treatment Period | | | | | Follow-up Period |
|---|-----------|--------------------------------|-------------------------------|---------|---------|----------|-----------------------|-------------------------------|
| | Wk -4 | Wk -2 [a] | Day 1 Baseline [b] | Wk 4 | Wk 8 | Wk 16 | Wk 24 or EOT/EW | 30 Days Post EOT/EW [c] |
| | - | ±3 | - | ±3 | ±3 | ±3 | ±3 | +7 |
| Initiation Activities | | | | | | | | |
| Informed consent/assent | X | | | | | | | |
| Assess inclusion/exclusion criteria | X | X | X | | | | | |
| Demography | X | | | | | | | |
| Complete medical history | X | X | | | | | | |
| Register patient for Screening in IXRS | X | | | | | | | |
| Register patient for Run-in in IXRS | | X | | | | | | |
| Randomization | | | X | | | | | |
| Procedures/Events | | | | | | | | |
| Complete physical examination [d] | X | | | | | | X | |
| Symptom-related brief physical examination [d] | | X | X | X | X | X | | |
| Weight [e] | X | X | X | X | X | X | X | |
| Height | X | | | | | | | |
| Vital signs [f] | X | X | X | X | X | X | X | |
| 12-lead ECG [g] | X | | X | | | | X | |
| Patient-centered Site Activities | | | | | | | | |
| Review SMBG and make adjustment to insulin dose as needed to meet ADA/EASD Guidelines | | | X | X | X | X | X | |
| Record insulin dose and SMBG data on the eCRF | | | X | X | X | X | X | |
| Dispense patient study diary and glucose testing strips (meter at first visit) [h] | | X | X | X | X | X | | |
| Dispense Ketostix® or similar to measure urine ketones for DKA assessment per Section 9.5.2 [i] | X | | | | | | | |
| Dispense BHB meter and testing strips | | X | | | | | | |
| Review study diary and record hypoglycemic symptoms or events | | | X | X | X | X | X | |
| Diet and exercise instruction [j] | X | X | | | | | | |

Statistical Analysis Plan

Version: Final 1.0

Lexicon Pharmaceuticals Protocol No. LX 4211.1-312-T1DM

Date of Issue: 17 MAR 2017

Covance Study ID: 000000145143

| Week/Visit Window (days) | Screening | Single-blind Placebo Run-in | Double-blind Treatment Period | | | | | Follow-up Period |
|---|-----------|--------------------------------|-------------------------------|---------|---------|----------|-----------------------|-------------------------------|
| | Wk -4 | Wk -2 [a] | Day 1 Baseline [b] | Wk 4 | Wk 8 | Wk 16 | Wk 24 or EOT/EW | 30 Days Post EOT/EW [c] |
| | - | ±3 | - | ±3 | ±3 | ±3 | ±3 | +7 |
| Recommendations on basic genitourinary hygiene, maintaining hydration and recognition of DKA and its management | | | X | X | X | X | | |
| Assess compliance | | | X | X | X | X | X | |
| Record concomitant medications [k] | X | X | X | X | X | X | X | |
| Record SAEs [l] | X | X | X | X | X | X | X | X |
| Record AEs [m] | | | X | X | X | X | X | X |
| Record EOSIs | | | X | X | X | X | X | X |
| Dispense single-blind placebo tablets | | X | | | | | | |
| Dispense Double-blind study drug | | | X | | X | X | | |
| Patient Reported Outcome (Patients in substudy only) | | | | | | | | |
| Dispense satiety daily diaries and review instruction for use [n] | | X | | | | X | | |
| Collect satiety daily diaries [o] | | | X | | | | X | |
| Laboratory/glycemic Assessments | | | | | | | | |
| A1C [p] | X | X | X | X | X | X | X | |
| Fingerstick glucose on site | X | X | X | X | X | X | X | |
| Fasting plasma glucose [p] | X | | X | X | X | X | X | |
| Fasting serum chemistry [p] | X | | X | X | X | X | X | |
| Fasting lipid profile [p] | X | | X | | X | | X | |
| BHB (central lab) | X | X | X | X | X | X | X | |
| BHB (point-of-care) | X | X | X | X | X | X | X | |
| Hematology | X | | X | | X | | X | |
| Urine albumin, calcium, glucose, creatinine | | | X | | | | X | |
| Urinalysis with microscopy | X | | X | | | | X | |
| Pregnancy test (serum) [q] | X | | | | | | | |
| Pregnancy test (urine) [q] | | | X | | | | X | |
| Follicle stimulating hormone (females only) [r] | X | | | | | | | |
| Thyroid stimulating hormone [s] | X | | | | | | | |

Statistical Analysis Plan

Version: Final 1.0

Lexicon Pharmaceuticals Protocol No. LX 4211.1-312-T1DM

Date of Issue: 17 MAR 2017

Covance Study ID: 000000145143

| Week/Visit Window (days) | Screening | Single-blind Placebo Run-in | Double-blind Treatment Period | | | | | Follow-up Period |
|---|-----------|--------------------------------|-------------------------------|---------|---------|----------|-----------------------|-------------------------------|
| | Wk -4 | Wk -2 [a] | Day 1 Baseline [b] | Wk 4 | Wk 8 | Wk 16 | Wk 24 or EOT/EW | 30 Days Post EOT/EW [c] |
| | - | ±3 | - | ±3 | ±3 | ±3 | ±3 | +7 |
| Fasting blood sample and random urine for storage | | | X | | | | X | |

A1C = hemoglobin A1C; ADA = American Diabetes Association; AE = adverse event; BHB = beta-hydroxy butyrate; BP = blood pressure; EASD = European Association for the Study of Diabetes; eCRF = electronic case report form; DKA = diabetic ketoacidosis; ECG = electrocardiogram; EOSI = Events of Special Interest; EOT = End of Treatment; EW = early withdrawal; IXRS = Interactive Voice/Web Response System; SAE = serious adverse event; SMBG = self-monitored blood glucose; Wk = Week

- a. The duration of the single-blind placebo Run-in Period is 14 days, ±3 days.
- b. All laboratory assessments occur prior to first dose of Double-blind study drug. All visit dates will be scheduled based on the date of randomization with a ±3 days visit window allowed.
- c. All patients will have a follow-up telephone contact 30 days after the last dose of study drug to collect information on any SAEs, any EOSI, or AEs that were ongoing at the time of the EOT/EW Visit.
- d. A complete physical examination will include, at minimum, a review of the patient's general appearance, head, eyes, ears, nose and throat, neck, heart, lungs, abdomen, back and extremities, skin, and general neurological system. A symptom related brief physical exam will only occur if the patient is experiencing symptoms or AEs. If a symptom related brief physical exam is required, it should include a review of all body systems that relate to the symptoms and/or AE the patient is experiencing.
- e. Patients should be weighed at approximately the same time of day, wearing minimal clothing, ie, no coat/shoes, using the same calibrated scale where possible.
- f. Vital sign measurements should be measured after the patient has been seated for at least 5 minutes and prior to phlebotomy.
- g. The 12-lead ECG recordings should be obtained prior to the morning study drug administration. ECG recording should be recorded either prior to phlebotomy or at least 30 minutes after phlebotomy.
- h. The patient will be provided with a study diary and glucose monitoring supplies for use at home. These supplies will be provided to all sites by the Sponsor.
- i. After the initial dispensation at the Screening Visit, additional Ketostix[®] (or similar) will be dispensed on an as needed basis.
- j. Counseling frequency may be increased at the discretion of the Investigator.
- k. Concomitant medications taken from 2 weeks prior to the Screening Visit through the EOT, including those specified in the inclusion/exclusion criteria, must be recorded in the source documents.
- l. All SAEs will be collected starting with signing informed consent/assent and continue until 30 days after the last dose of study drug.
- m. The collection of AEs will start after the first dose of Double-blind study drug. All AEs ongoing at the EOT/EW visit should be followed for at least 30 days following the last dose of study drug or until the event has resolved, the condition has stabilized, the etiology of the event is determined to be not related to study drug, or the patient is lost to follow-up.
- n. Patients participating in the satiety substudy will be instructed to complete their satiety daily diaries before the first meal of the day. The patients will be instructed to complete the diaries each day during the 14day, ±3 days single-blind placebo Run-in Period and each day for the last 14 days, ±3 days of the Double-blind Treatment Period (during Week 23 and Week 24).
- o. Entries on the satiety daily diaries should be reviewed and recorded on the eCRF.

Statistical Analysis Plan

Version: Final 1.0

Lexicon Pharmaceuticals Protocol No. LX 4211.1-312-T1DM

Date of Issue: 17 MAR 2017

Covance Study ID: 000000145143

- p. Fasting blood samples should be taken after the patient has fasted for at least 8 hours; patients should only drink water or noncaffeinated, zero-calorie beverages. If the patient is unable to fast as above, the scheduled “fasting” laboratory samples will still be collected, and the non-fasting status will be noted in the eCRF.
- q. Serum pregnancy test must be performed at Screening, and the result reviewed prior to beginning the single-blind Run-in Period for all females with childbearing potential unless there is documented history of menopause or they are surgically sterile. All other required pregnancy tests can be performed via a urine test. Baseline urine test result must be reviewed prior to Randomization. The Investigator may perform additional tests at their discretion or as required by local regulations.
- r. If necessary, follicle-stimulating hormone will be measured at Screening to confirm postmenopausal status.
- s. If abnormal, free thyroxine will be measured.

Statistical Analysis Plan

Version: Final 1.0

Lexicon Pharmaceuticals Protocol No. LX 4211.1-309-T1DM

Date of Issue: 17 MAR 2017

Covance Study ID: 000000145143

